5.1.1.8 Able to adhere to the study visit schedule and other protocol requirements

5.1.1.9 All men and women must agree to practice effective contraception during the study period if not otherwise documented to be infertile.

5.1.2 Exclusion Criteria

5.1.2.1 Patients with history of second malignancy are eligible if they have documentation of disease stability, off therapy, based on CT scan or other measures for the 6 months prior to entry in core.

5.1.2.2 Any serious medical condition or psychiatric illness that would prevent the patient from providing informed consent.

5.1.2.3 Chemotherapy or other investigational anticancer therapeutic drugs in the two weeks prior to study entry; in the event of rapidly proliferative disease, however, the use of hydroxyurea is permitted up to 24 hours before study entry in core

5.1.2.4 Evidence of active CNS leukemia

5.1.2.5 Pregnant or lactating women

5.1.2.6 Uncontrolled infection; to be eligible, patients receiving treatment for an infection (antibiotic, antifungal or antiviral treatment) must be afebrile ($<38.3^{\circ}\text{C}$) and without hemodynamic instability or dyspnea from pneumonia for >48 hrs prior to the start of induction therapy.

5.1.2.7 Hypersensitivity to cytarabine, daunorubicin or liposomal products

5.1.2.8 History of Wilson's disease or other copper-metabolism disorder

5.2 Withdrawal of Patients

Patients will be discontinued from treatment and begin follow-up for survival under the following circumstances:

- Persistent disease: lack of a response to treatment after two cycles of induction therapy
- Relapsed disease: re-appearance of disease following CR or CRI
- Unacceptable toxicity
- Patient non-compliance with protocol
- Administration of non-protocol chemotherapy
- Intercurrent illness which, in the judgment of the investigator, affects assessment of clinical status to a significant degree, and requires discontinuation of protocol therapy.

During any phase of the study, if a patient requests termination of treatment and/or follow-up, the patient will be discontinued and no further information collected. The patient will be classified as withdrawal of consent.

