4.0 Study Design

One cycle equals 28 days.

This study is an open-label, two-arm or possibly 3-arm, phase II trial. CPX-351 is administered as approximately a 90-minute infusion on days 1, 3, and 5 with one study arm receiving 50 units/m² and the other receiving 75 units/m². Both the 50 and the 75 unit/m² dose levels are considered to have acceptable safety based on observations from a pair of randomized Phase II studies conducted in adult patients, where the observed 60-day mortality results in patients considered fit for intensive chemotherapy and with no prior history of stem cell transplant, was observed to be reduced compared to control.

Patients with newly diagnosed AML who are predicted to be at high risk (30-50%) for induction mortality (death by day 60) are eligible. Every patient entered must have at least one AML-related factor (adverse cytogenetics, secondary AML, MDR phenotype, etc.) that contributes to elevated risk of induction mortality. Patients may or may not have patient-related factors (poor performance status, co-morbidities, poor organ function, etc.) that also contribute to elevated risk of induction mortality. 30 patients will be randomized with a 1:1 ratio to the two dose arms with 15 patients per arm to assess for safety and efficacy. If safety is demonstrated for both of the sub-MTD dose levels, and escalation is deemed feasible above 75 units/m², a cohort of 15 patients will be studied at 100 units/m², the MTD dose level. The latter dose (i.e., 100 units/m²) was found safe and an additional 25 patients will be enrolled at this dose (for a total of 40 evaluable patients) to define efficacy at this standard dose.

At the end of the study a single dose level will be confirmed to have acceptable safety if the observed rate of dose limiting toxicity (DLT) is <5 DLT/15 patients.<33%). Dose limiting toxicity is defined as induction mortality (death occurring during the first 60 days from start of study therapy), grade 3 or 4 non-hematologic toxicity, or dose limiting

hematologic toxicity at least possibly related to the study drug occurring during the first 60 days from the start of study therapy (i.e., during the first cycle of therapy).

For non-hematologic toxicity the following are counted as dose limiting toxicities only under the conditions noted:

- Liver toxicity: Grade 4, related to the study drug, not resolving to grade 2 within 7 days.

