6.3 Early Termination or End of Treatment

Any patient that completes or discontinues treatment must have the following evaluations performed within 30 days after termination and prior to the initiation of any salvage therapy, if not performed within the last 30 days:

Procedure	Evaluation	Timing
Physical exam	Objective review of body systems ECOG Performance Status	Within 30 days after discontinuation
Vital signs	Heart rate Blood pressure Temperature Respiratory rate	Within 30 days after discontinuation
Hematology	Hemoglobin White Blood Count Platelets Differential Count (may be omitted if WBC $\leq 0.5 \times 10^9/L$)	Within 30 days after discontinuation
Biochemistry	BUN Creatinine Electrolytes (Sodium, Potassium, Chloride) Bilirubin AST or ALT	Within 30 days after discontinuation
Diagnostic Imaging	Echocardiography/MUGA	Within 30 days after discontinuation if a study has not been performed since last treatment but before the initiation of any non-protocol treatment
ECG		Within 30 days after discontinuation
Copper levels	Serum Copper	Within 30 days after discontinuation if a study has not been performed since last treatment
Adverse Events/Toxicity	CTCAE v.4 assessment	Assess Adverse events that were ongoing at the time of discontinuation and record and report any new serious adverse events (up to 30 days after discontinuation)
Correlative studies (optional)*	BNP, Troponin I, high-sensitivity troponin (I or T)	Within 30 days after discontinuation

* Failure to collect samples for optional studies will not constitute a protocol deviation.

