7.5 Duration of Protocol Treatment

Patients may continue on study provided they have not met the criteria for discontinuation of therapy (See Section 5.2). The table below summarizes the expected duration of the Treatment Phase. Patients may receive up to two induction courses followed by consolidation courses. After the Treatment Phase, patients are followed until death.

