8.2 Overall Survival

All enrolled patients are assessed for overall survival. Overall survival is measured from the date of registration to death from any cause, patients not known to have died at last follow-up are censored on the date they were last known to be alive.

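### Read literally, Section 5.2 ends all data collection when a patient asks only to stop treatment, so a Day-60 death that counts as a DLT can go unrecorded, and no rule says how unknown status is counted

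*Combined protocol and SAP*

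**What the plan says.** Section 5.2 has two parts. The first lists six reasons for stopping treatment, among them persistent disease, unacceptable toxicity, non-compliance and intercurrent illness, under the lead "Patients will be discontinued from treatment and begin follow-up for survival under the following circumstances". The second deals with the patient's own request: "if a patient requests termination of treatment and/or follow-up, the patient will be discontinued and no further information collected". It adds: "The patient will be classified as withdrawal of consent". A patient's request is not among the six reasons that lead to survival follow-up.

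Other sections carry no such exception:
- Section 6.3: "Any patient that completes or discontinues treatment must have the following evaluations performed within 30 days after termination".
- Section 7.5: "After the Treatment Phase, patients are followed until death".
- Section 8.2: "All enrolled patients are assessed for overall survival".

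The outcome affected is defined in Section 4.0: "Dose limiting toxicity is defined as induction mortality (death occurring during the first 60 days from start of study therapy", alongside specified non-hematologic and hematologic toxicities. Day-60 induction mortality is also named in the secondary objectives (Section 3.2). Under Section 9.2.2, serious adverse events are captured until 30 days after the last dose, unless the patient withdraws consent.

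**The concern.** Because the trigger covers treatment, follow-up or both, a patient who declines further drug but would accept a telephone call about survival is treated like one who refuses all contact. A non-compliant patient is followed for survival; a patient who asks to stop is not. If such a patient dies before Day 60, the death meets the DLT definition, yet the site has been told to collect nothing more.

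The serious-adverse-event route does not fill the gap. The withdrawal-of-consent label closes it. Even without that label, the routine window after a single induction ends on about Day 35 (last dose on Day 5, plus 30 days), short of Day 60.

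DLT counts drive the stopping boundaries in Tables 8, 11 and 12 and the end-of-study rule of fewer than 5 DLTs in 15 patients (Section 4.0). The population is selected for a 30-50% predicted risk of death by Day 60 (Section 3.1), and the initial cohorts have 15 patients each. A few uncollected deaths could therefore change a decision.

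**Working it through.** **Inputs.** DLT prior Beta(0.66, 1.34); stop when Pr(T > 0.33 | data) > 0.85; Table 8 stops at 4 or more of 5, or 6 or more of 10 (all Section 10). A dose is acceptable with at most 4 DLTs in 15 (Section 4.0). The documents give no withdrawal rate.

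**Reproducing the plan.** With x DLTs in n patients the posterior is Beta(0.66 + x, 1.34 + n − x). Its probability above 0.33 is:
- 3/5: 0.847; 4/5: 0.967
- 5/10: 0.837; 6/10: 0.944

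The first counts above 0.85 are 4/5 and 6/10, as in Table 8. Applying the futility and toxicity rules together, with response and DLT independent, gives early stopping of 0.543 at a response rate of 0.3 and a DLT rate of 0.5, as in Table 9.

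**How unknown status is handled.** Sections 9.1 and 10 make every dosed patient evaluable for toxicity. Section 10 counts patients lost in the first two cycles as failures, but only in the efficacy analysis. Section 4.4 replaces patients who leave before DLT assessment because of progressive disease or unrelated intercurrent illness; it does not name patient request. Take 10 patients with 6 true DLTs, one of them an unseen death:
- counted as no DLT: 5/10 = 0.837, continue
- dropped: 5/9 = 0.892, above the cutoff
- replaced: 5/10 or 6/10, depending on the replacement's outcome

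The same patients can give opposite decisions under rules the plan does not choose between. One unseen death counted as none also reverses the decision at the other boundaries checked: 4/5 to 3/5 (0.967 to 0.847), and in Table 11 8/15 to 7/15 (0.934 to 0.842) and 10/20 to 9/20 (0.930 to 0.8495).

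**Illustration of size.** Assume a true DLT rate of 0.50, a fraction w of patients withdrawing at average risk, and all their DLTs unseen and counted as none. The observed rate is p = 0.50 − 0.50w, which is 0.45 at w = 10% and 0.40 at w = 20%.

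The chance of a Table 8 toxicity stop by n = 10 is P(X₅ ≥ 4) + Σ P(X₅ = x)·P(Y₅ ≥ 6 − x) over x = 0 to 3, where X₅ and Y₅ are DLT counts in the first and second five patients. At p = 0.50 this is 6/32 + (5 + 60 + 160)/1024 = 0.407. The chance of passing the safety rule at a fixed n = 15 is P(X ≤ 4); at p = 0.50 this is 1941/32768 = 0.059.

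| w | observed p | toxicity stop by n = 10 | at most 4 of 15 |
|---|---|---|---|
| 0 | 0.50 | 0.407 | 0.059 |
| 10% | 0.45 | 0.291 | 0.120 |
| 20% | 0.40 | 0.193 | 0.217 |

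If half of the withdrawn patients' DLTs had been recorded before the request, then at w = 10% p = 0.50 − 0.10 × 0.50 × 0.5 = 0.475, giving 0.348 and 0.086.

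For the 100 units/m² arm, the same enumeration over the Table 12 toxicity boundaries (looks at 5 to 35 patients) gives 0.72 at p = 0.50 and 0.51 at p = 0.45.

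**The case against.** The strongest reply is that this is a wording conflict and not proven data loss. The sentence ends by classifying the patient as a withdrawal of consent, so it may have been meant only for patients who withdraw consent, for whom stopping collection is normal. Sections 6.3, 7.5 and 8.2 point that way, and the consent pages are not available to settle it. This stands as a caution: the literal reading is one reading, but it is the one a site would find in the withdrawal section.

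Second, patients doing badly often have other routes out, such as toxicity or intercurrent illness, which keep survival follow-up. First-induction dosing ends on Day 5 and a second induction is optional, so declining it need not be coded as a request to terminate. This limits how often the problem arises; it does not remove it.

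Third, the attribution phrase in the DLT definition might be read as covering deaths too. Even so, a death must be known before it can be attributed.

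Fourth, any boundary in a small sample is fragile to one miscount, and the withdrawal rates are assumed. Both are true. The single-death reversals do not depend on those rates, but they do depend on an unseen death being counted as no DLT.

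A reader might go further and infer that those who ask to stop are the patients most likely to die, so that each dose will look safer and survival longer. The documents give no data on those patients' prognosis. The direction of bias depends on the unstated handling rule, since dropping the patient leaves 5/9 above the cutoff.

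**Conclusion.** The point holds in a limited form. As written, Section 5.2 lets a treatment-only request end collection of Day-60 vital status, serious adverse events and survival, and it contradicts Sections 6.3, 7.5 and 8.2. The harm falls mainly on DLT and Day-60 mortality monitoring: Tables 8, 11 and 12 and the fewer-than-5-of-15 rule.

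The documents do not support extending it further. Response is protected by the failure rule. DLTs recorded before the request are kept. Survival is censored at the date last known alive (Section 8.2), possibly informatively, but it is not a listed objective and drives no stated decision.

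On size, one unseen death counted as no DLT is enough to turn a Table 8 stop into a continue at either look. The larger shifts in operating characteristics rest on a 50% true DLT rate, on withdrawal of 10% or 20% at average risk, and on all those DLTs being unseen and counted as none. They shrink if some were recorded before the request.

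**What to change.** 1. In Section 5.2, separate two events. After a request to stop study treatment only, perform the Section 6.3 evaluations and continue collecting response, Day-60 vital status and DLT, relapse and survival. End collection only when the patient explicitly withdraws from follow-up, and keep the data already collected. Record the two events separately on the case report form.
2. Reconcile Section 5.2 with Sections 6.3, 7.5, 8.2 and 9.2.2, so that a treatment-only stop does not close serious-adverse-event capture.
3. In Section 10, state how unknown Day-60 status is counted in the DLT rule, and whether Section 4.4 replacement applies to patients who leave at their own request.

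Taking vital status from public records, where allowed, is optional. The cost is a revised paragraph in Section 5.2, a sentence in Section 10, matching wording in the other sections, and one case report form field. Follow-up uses visits and survival contacts already planned. The change concerns data collection only and does not alter when treatment stops.

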6.0 Treatment of Patients

See APPENDIX 1: Patient Evaluation Flow Sheet

Copper Levels: MDACC will draw the serum copper, send it out for processing and will report the results in clinic station in approximately 4 days. This will be included in the budget for the cost incurred by the MDACC lab. MDACC will be reimbursed by the Supporter of this study (Jazz Pharmaceuticals) for this test.

6.1 Pre-Treatment Evaluations

The date of the first test or exam will be considered as date of the screening visit.

Procedure	Evaluation	Timing
Informed Consent	It should be personally signed and dated by the patient. The investigator must also personally sign and date the document. A copy of the Informed Consent must be given to the patient. The patient's study screening must be conspicuously noted in the source documentation.	Informed consent should be obtained prior to initiation of screening procedures. If the period between ICF signature date and screening visit is ≥ 30 days the patient must sign another ICF.
Demography	Date of birth, sex Basis for high risk of induction mortality	Within 14 days prior to registration in core
Medical History	Complete medical history	Within 14 days prior to registration in core
Physical Exam	Objective review of body systems ECOG Performance Status	Within 3 days prior to registration in core
Vital Signs	Heart rate Blood pressure Temperature Respiratory rate	Within 3 days prior to registration in core
Hematology	Hemoglobin White Blood Count Platelets Differential Count (may be omitted if WBC $\leq 0.5 \times 10^9/L$)	Within 1 day prior to registration in core
Biochemistry	BUN Creatinine Electrolytes (Sodium, Potassium, Chloride) Bilirubin AST or ALT	Within 1 day prior to registration in core
Bone Marrow Aspiration and/or Biopsy	Morphology	Within 14 days prior to registration in core
Copper levels	Serum copper	Within 14 days prior to registration in core

Procedure	Evaluation	Timing
Diagnostic Imaging	Chest X-ray Echocardiography or MUGA scan	Within 28 days prior to registration in core
ECG		Within 14 days prior to registration in core
Cytogenetics	Cytogenetics (performed locally) Molecular abnormalities: Evaluation of CEBPA, FLT3, and NPM1	Within 3 months prior to registration in core: patients may be registered and treated prior to the cytogenetic test results; however, every attempt should be made to have the results prior to registration in core
Correlative studies (optional)*	Immune reconstitution	Before the start of induction therapy
Correlative studies (optional)*	BNP, Troponin I, high-sensitivity troponin (I or T)	Before the start of induction chemotherapy
Correlative studies (optional)*	Pharmacodynamics	Before the start of induction chemotherapy
Pregnancy Test	Urine or serum pregnancy test	Within 7 days prior to registration in core

* Failure to collect samples for optional studies will not constitute a protocol deviation.

6.2 Evaluation during Treatment

Inductions and consolidations are administered as courses. A course consists of the administration of therapy with scheduled assessments to evaluate the response to treatment. The first induction may end before the completion of all evaluations if a second induction is necessary, (see Section 4.5). Induction is completed when a patient has

- A confirmed CR (see section 8.4)
- A CRi (see section 8.4) and is to begin consolidation treatment before documentation of hematologic count recovery
- Persistent/recurrent disease (PD/relapse)
- Response evaluation cannot be performed because of the patient's condition and no further study treatment can or will be administered.

Patients with a CR or CRi may receive consolidation treatments. Evaluations on Days 1-10 must be performed on the day indicated (± 2 day); all other evaluations are to be performed on the Study Day indicated ± 3 days, except when specifically indicated. Each course requires the following evaluations:

Procedure	Evaluation	Timing
Physical Exam	Objective review of body systems	Days 14 and 42
Vital Signs	Heart rate Blood pressure Temperature Respiratory rate	Days 14 and 42

Procedure	Evaluation	Timing
Hematology	Hemoglobin White Blood Count Platelets Differential Count (may be omitted if WBC $\leq 0.5 \times 10^9/L$)	Days 1, 3, 5, 7, 10 ± 2 , 14 ± 3 , then weekly (± 3 days) until Day 42 or peripheral blood count recovery
Biochemistry	BUN Creatinine Electrolytes (Sodium, Potassium, Chloride) Bilirubin AST or ALT	Days 1, 3, 5, 7, 10 ± 2 , 14 ± 3 , then weekly (± 3 days) until Day 42
Copper levels	Serum Copper	Perform prior to next treatment course
Bone Marrow Aspiration and/or Biopsy	Morphology	Day 28 (± 7 days) after every induction.
Cytogenetics	Cytogenetics (performed locally) Molecular abnormalities: Evaluation of CEBPA, FLT3, and NPM1	Required in patients with a CR or CRI with positive baseline findings (perform at the time of bone marrow assessment for CR or CRI). Optional in patient with normal findings at baseline
Diagnostic Imaging	Echocardiography or MUGA scan to assess LVEF	Prior to every other course of treatment after the cumulative DNR dose exceeds 300 mg/m ² , prior to every course of treatment after the cumulative DNR dose exceeds 500 mg/m ² , or 30 days after the last course.
Response Assessment		See Section 8.4.1
Adverse Events/Toxicity	CTCAE v.4 assessment	Beginning at the start of the first infusion, continually assess during Treatment Period and record and report any new serious adverse events (up to 30 days after completion of Treatment Period)
Concomitant Medications		Continually assess during Treatment Period
Correlative studies (optional)*	Immune effects	Before induction and at start of 1 st and 2 nd consolidation
Correlative studies (optional)*	BNP, Troponin I, high-sensitivity troponin (I or T)	Before the start of each cycle, and approximately 24 hrs from end of infusion on day 1 and day 5 of each cycle, and approximately on day 14 (± 4 days) of each cycle, end of treatment.
Correlative studies (optional)*	Pharmacodynamics	Pre-dose and 24-hrs (± 4 hrs) after first dose.

* Failure to collect samples for optional studies will not constitute a protocol deviation.

6.3 Early Termination or End of Treatment

Any patient that completes or discontinues treatment must have the following evaluations performed within 30 days after termination and prior to the initiation of any salvage therapy, if not performed within the last 30 days:

Procedure	Evaluation	Timing
Physical exam	Objective review of body systems ECOG Performance Status	Within 30 days after discontinuation
Vital signs	Heart rate Blood pressure Temperature Respiratory rate	Within 30 days after discontinuation
Hematology	Hemoglobin White Blood Count Platelets Differential Count (may be omitted if WBC $\leq 0.5 \times 10^9/L$)	Within 30 days after discontinuation
Biochemistry	BUN Creatinine Electrolytes (Sodium, Potassium, Chloride) Bilirubin AST or ALT	Within 30 days after discontinuation
Diagnostic Imaging	Echocardiography/MUGA	Within 30 days after discontinuation if a study has not been performed since last treatment but before the initiation of any non-protocol treatment
ECG		Within 30 days after discontinuation
Copper levels	Serum Copper	Within 30 days after discontinuation if a study has not been performed since last treatment
Adverse Events/Toxicity	CTCAE v.4 assessment	Assess Adverse events that were ongoing at the time of discontinuation and record and report any new serious adverse events (up to 30 days after discontinuation)
Correlative studies (optional)*	BNP, Troponin I, high-sensitivity troponin (I or T)	Within 30 days after discontinuation

* Failure to collect samples for optional studies will not constitute a protocol deviation.

6.4 Evaluation during Long-term Follow-up

The following evaluations are completed during the follow-up phase (i.e., after completion of all therapy to continue for one year except for survival and relapse status which will continue until death and relapse, respectively):

Procedure	Evaluation	Timing
Patient status report	Survival status	Until death
	Relapse status New anti-leukemic therapies	Monthly until relapse or the initiation of new therapy
Hematology	Hemoglobin Hematocrit Red Blood Count White Blood Count Platelets Differential Count (may be omitted if WBC $\leq 0.5 \times 10^9/L$)	Every 2-3 months for one year until relapse or the initiation of new therapy, then as clinically indicated.
Bone Marrow Aspiration and/or Biopsy	Morphology	Every 3-4 months. For patients in CR, consider performing if peripheral blood counts fall below 1000/ μL for ANC or 100,000/ μL for platelets for >1 month with no obvious explanation for the drop or at any time there is suspicion of relapse; for patients in CRI perform if counts fall significantly below peak recovery. If the peripheral blood counts in a patient with a CRI recover to CR levels ($\geq 1000/\mu L$ for ANC or $\geq 100,000/\mu L$ for platelets), consider performing a bone marrow evaluation to confirm full CR. Following the first year of follow up, aspirations will be done as clinically indicated; record relapse information, including any bone marrow evaluations. Not required following the initiation of new therapy and or relapse.
Diagnostic Imaging	Echocardiography or MUGA	Perform every 3-4 months if last Treatment Phase LVEF was reduced >10% from baseline and is less than 50%. Continue assessments until LVEF returns to baseline or until 1 year from start of therapy.
Biochemistry	BUN Creatinine Bilirubin AST or ALT	Every 2-3 months for one year until relapse or the initiation of new therapy, then as clinically indicated.
Copper levels	Serum Copper	Perform monthly only if elevated copper (>20% above ULN) present at EOT. Perform every 1 month until abnormality returns to within 20% of ULN, or until 1 year, or the initiation of new therapy, or relapse (whichever is earliest)

